### ***3.1. Duration of Study***

Each subject will perform a pre-study evaluation, train using one of the protocols for three to twelve months, perform a post study evaluation as well as one and six month retention evaluations.

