targeted to train movement of their shoulder, elbow and fingers. The physical therapist will set up the apparatus in their home and visit them once or twice in the first week to train them how to use the system and how to play the games. After this training period they will then continue to practice in their homes independently with on-line support from the therapist and in-person or on-line assistance from the study-engineer as needed. Both groups will be instructed to perform all three of the simulations assigned to them for at least twenty minutes, daily for twelve weeks.

**Figure 5.** Left: Patient home system setup with the passive arm support, hand tracking device and computer. Right: Patient is able to talk to and see therapist (lower left corner) and while playing games, patient's game screen is shared with therapist at the same time as well.

(career score) on that simulation, and the top ten career scores for the entire program (including other subjects). When users achieve a

The enhanced motivation (EM) group will train using three simulations (See Table 2). These simulations will all provide the user with eight to twelve levels of gradually increasing difficulty and complexity. There is a screen announcing each level change and the graphics for each new level change substantially. Scoring opportunities increase at each new level as well. When a simulation is completed, for the day, a leaderboard displays the user's score for the day, their total points scored for the entire training period

milestone career score (1 million points, two million points, three million points), they will have an opportunity to choose a new avatar for future play. This opportunity is provided at the beginning of gameplay.

The unenhanced control (UC) group will perform the same three simulations. Difficulty will increase utilizing an adaptive control algorithm that increases difficulty based on performance. Difficulty changes are extremely incremental making them imperceptible for most subjects. Graphics and scoring will not change as difficulty level changes. Total score for the day will be displayed after each simulation for the day is completed, but no leaderboard displaying past performances, career scores or the career scores of other subjects will be displayed. UC subjects will use the same avatars for the entire experiment.

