## Experimental Design and Training Protocol

### **Aim 1: To test the impact of motivation enhanced, game-based interventions on intrinsic motivation to perform a telerehabilitation exercise program in persons with strokes.**

**Rationale:** Low levels of motivation are cited as the primary barrier to adherence to home based rehabilitation programs. Designing rehabilitation activities that elicit the highest levels of intrinsic motivation is critical to overcoming this barrier and optimizing the effectiveness of home based interventions.

**Hypotheses:** We predict that subjects in the motivation enhanced (ME), game-based intervention group will report higher initial levels of motivation as measured by the Intrinsic Motivation Inventory than those performing un-enhanced control (UC) interventions. We further predict that IMI scores for the ME group will remain higher than those for the UC group.

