**Outcomes Measures:** (See Table 4 for a summary of all measures and Figure 6 for a data collection Schedule). The impact of game mechanics on motivation to perform the simulation that is specifically related to

the experience of using the simulation not the general motivation to improve their hand function or increase their independence, etc. will be measured utilizing the Intrinsic Motivation Inventory (IMI) (58). IMI data will be measured following the first training session (Collection 2) to measure the subjects' initial reaction to the system and simulations as well as after the twelfth session (Collection 3) and after the final training session (Collection 4) to chart subjects' responses to repeated use.

*Statistical Analysis:* (See Table 5 for a summary of all planned comparisons) Our primary outcome measures will compare differences in IMI scores after the initial exposure to the training program. Data will be evaluated for normality and transformed if necessary for evaluation. Baseline group equivalence will be evaluated via t-test. The within-and-between group interaction will be examined to evaluate differences in change between groups.

**Aim 2: To test the impact of intrinsic motivation on adherence to a telerehabilitation exercise program in persons with strokes.**

**Table 4** Outcome measures

Motivation Measure	
Intrinsic Motivation Inventory	Measurement of emotional response to an activity.
Adherence Measures	
Number of interventions days	Recorded by system
Total intervention time	Recorded by system
Average intervention day time	Recorded by system
Clinical Measures	
Upper Extremity Fugl-Meyer Assessment (66)	A 33 item battery which evaluates reflexes, movement patterns in and out of synergy, grasp, and coordination (impairment level)
Action Research Arm Test (62)	19 item battery which tests the ability to handle items of different size, shape and weight (activity level)
Box and Blocks Test (67)	Standardized dexterity test with well-established benchmarks for persons with CVA and age-matched healthy populations
Quality of Life Measure	
Stroke Impact Scale (69)	Patient reported assessment of multiple activity and participation level domains post stroke including hand function, activities of daily living and social participation.
Kinematic/Kinetic Measures	

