Hand opening/closing range of motion	Sum of maximum angular excursions of the paretic metacarpophalangeal (MCP), proximal inter-phalangeal (PIP) and distal inter-phalangeal joints (DIP) joints.
Hand opening velocity	Peak angular velocity during hand opening
Hand trace RMSE	Ability to control hand opening as subject moves a cursor tracking a sine wave. Reported as root mean square error (RMSE) comparing target position and cursor position.
Wrist Trace RMSE	Ability to control wrist flexion and extension as subject moves a cursor tracking a sine wave. Reported as root mean square error (RMSE) comparing target position and cursor position.
Horizontal shoulder and elbow trace RMSE	Ability to control shoulder and elbow as subject moves a cursor tracking a sine wave. Reported as root mean square error (RMSE) comparing target position and cursor position.

*Rationale:* Very few rehabilitation studies examine the interaction between motivation and adherence quantitatively. Utilizing knowledge of this interaction to inform design of rehabilitation simulations should advance the field of home based rehabilitation substantially.

*Hypothesis:* We predict that intrinsic motivation related to game play will predict adherence more effectively than patient readiness alone.

*Subjects:* The same subjects will be utilized for all three aims.

*Outcome measurements:* will include number of sessions as well as total intervention time and average session time. Time signatures from the telerehabilitation system will be used to overcome overestimation effects associated with patient self-reports of actual exercise time (59).

In an attempt to expand our understanding of the interaction between motivation (as measured by the IMI) and adherence to the autonomous home rehabilitation program, we will perform an in depth qualitative analysis focusing on subjects' unique perceptions and understandings of their participation in the proposed rehabilitation program. Using a Grounded Theory approach (60, 61), data collection and analysis will follow

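### IMI Collection 3 is timed by session count and Collection 4 by an undefined final session, so the later motivation data depend on adherence

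*SAP*

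**What the plan says.** SAP Aim 1, Outcomes Measures, sets three IMI points, each triggered by a session. The first: "IMI data will be measured following the first training session (Collection 2". The other two come "after the twelfth session (Collection 3) and after the final training session (Collection 4". The stated purpose of the later points is to follow how subjects react as use continues.

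The SAP's Treatment Protocol prescribes practice "for at least twenty minutes, daily for twelve weeks", and after the first-week visits "After this training period they will then continue to practice in their homes independently", with on-line support. Protocol section 3.1 instead has subjects "train using one of the protocols for three to twelve months".

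Number of sessions is an Aim 2 adherence outcome, and Table 4 lists number of intervention days. The Aim 1 rationale names low motivation as the main barrier to adherence. The Aim 2 hypothesis reads: "We predict that intrinsic motivation related to game play will predict adherence more effectively than patient readiness alone".

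Collections 3 and 4 serve the second Aim 1 hypothesis, "We further predict that IMI scores for the ME group will remain higher than those for the UC group", and the group-by-time interaction. The primary Aim 1 comparison uses IMI after initial exposure. The Aim 2 regression names IMI from Data Collection 1.

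The readable text gives no calendar window, no fallback for a subject who never reaches session 12, no definition of the final session, and no handling of missing or off-schedule IMI. Figure 6 (schedule) and Table 5 (planned comparisons) are cited but not visible in the text supplied.

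**The concern.** The trigger for measuring motivation is a quantity that motivation is expected to determine. After the first week subjects set their own pace, so on the SAP's own theory a less motivated subject reaches Collection 3 later, or not at all. If the enhanced games work as predicted, this happens more often in the un-enhanced control (UC) arm than in the motivation-enhanced (ME) arm.

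Two things follow for the sustained-difference hypothesis and the interaction. First, Collection 3 is not one point in time: elapsed time since first exposure varies with adherence and possibly by arm. Second, those with a Collection 3 value are selected on motivation. Dropping the least motivated subjects, more of them from UC, makes motivation look better sustained in both arms and narrows the contrast between them.

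Collection 4 has a different problem. The final session could mean the end of the programme or the last session a subject actually did, and the two readings put an early stopper's measurement at very different times.

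**Working it through.** The plan states no figure on this point, so there is nothing to reproduce. There are three steps.

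**1. When Collection 3 falls.** Inputs: 12 sessions (SAP Aim 1) and daily practice for 12 weeks (SAP Treatment Protocol), so 12 × 7 = 84 planned sessions. Assumed: one session per practice day and a steady pace of r sessions a week. Day of twelfth session = (12 / r) × 7. Gap to programme end = 84 − that day.

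| Sessions/week | Day of session 12 | Days left to day 84 |
|---|---|---|
| 7 | 12 | 72 |
| 5 | 16.8 | 67.2 |
| 3 | 28 | 56 |
| 2 | 42 | 42 |
| 1 | 84 | 0 |

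At one session a week, Collections 3 and 4 coincide. Below 12 / 84 = 14.3% of planned sessions, Collection 3 never happens. If each day carries an independent probability p of practice (assumed), the binomial chance of at least 12 sessions in 84 days is about 1.00 at p = 0.30, 0.93 at 0.20, 0.62 at 0.15, 0.13 at 0.10 and 0.001 at 0.05. Late measurement therefore needs only practice below daily. Absent measurement needs very low adherence, or stopping before session 12.

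**2. When Collection 4 falls.** If final means programme end, it is at about day 84 for everyone. If it means the last session done, a subject who stops on day 14 is due on day 14. That is early, and staff can recognise it as the last session only afterwards, so it may be missed.

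**3. Size of the selection at Collection 3 (all inputs assumed).** IMI in SD units is N(0, 1) in UC and N(0.5, 1) in ME. P(reach session 12) = 1 / (1 + exp(−(a + b × IMI))), with a set to give the stated average reach over both arms. Observed difference = mean IMI of ME reachers − mean IMI of UC reachers, by numerical integration.

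| Average reach | Slope b | ME mean − UC mean among reachers | Loss from 0.5 SD |
|---|---|---|---|
| 95% | 1.0 | 0.537 − 0.057 = 0.48 | 4% |
| 90% | 0.5 | 0.544 − 0.054 = 0.49 | 2% |
| 80% | 1.0 | 0.645 − 0.201 = 0.44 | 11% |
| 80% | 2.0 | 0.702 − 0.320 = 0.38 | 24% |
| 70% | 2.0 | 0.802 − 0.448 = 0.35 | 29% |

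In the 80%, slope 2.0 case, 75% of UC and 85% of ME reach session 12. The observed mean is too high by 0.32 SD in UC and by 0.702 − 0.5 = 0.20 SD in ME, and 0.32 − 0.20 = 0.12 SD is the lost contrast. A second model, with adherence correlated 0.3 to 0.7 with IMI and 10% to 30% of UC not reaching session 12, gives 0.39 to 0.49 SD.

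For scale: if the SAP's 30 subjects split equally, the standard error of a difference is √(2/15) = 0.37 SD and the 95% half-width is 2.05 × 0.365 = 0.75 SD. Biases of 0.01 to 0.15 SD are then about 0.03 to 0.4 standard errors.

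**The case against.** The best defence is that counting sessions is deliberate. The IMI here asks about the experience of using the simulation, and equal exposure suits the aim of following reactions to continued use. A pure day-14 rule would compare a subject with 14 sessions to one with 4, and exposure would then differ by arm if the hypothesis holds. This stands as a reason not to discard session 12. It does not answer the selection problem, because exposure is equal only among those who persist.

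The defence can also point to remote monitoring, a video link and therapist support, which make fewer than 12 of 84 sessions unlikely. The documents give no expected adherence, so this can be neither confirmed nor dismissed. If it is right, the loss is a few per cent. In these models the bias also runs against the sponsor's hypothesis and is small beside the sampling error of a 30-subject trial. Both points stand, and they limit how serious this is.

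Lastly, SAP Aim 3, Outcome Measures, has a research assistant collect every Table 4 measure before training, immediately after it and 3 months later. Table 4 includes the IMI, so read literally there is an IMI tied to the end of training. But that schedule labels its points Data Collections 1 and 2, which does not match Aim 1's numbering. It is a conflict to resolve and does not clearly supply the missing rule.

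**Conclusion.** The concern holds for Collection 3: its timing runs from day 12 to day 84 over the paces considered, and its availability depends on completing at least 12 of 84 planned sessions. For Collection 4 the fault is an undefined trigger. The consequence is confined to the sustained-difference hypothesis and the interaction. The range of 0.35 to 0.49 SD for a true 0.5 SD illustrates what selection could do under assumed reach and slope. It is not an estimate for this trial.

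A reader might infer more in three ways that the documents do not support:

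- That low adherers have both later collections late or missing. Everyone who trains has a last session, so an early stopper is due for Collection 4 early, or at about week 12 if final means programme end. A miss is possible, but the text does not imply it.
- That the main motivation result is compromised. The primary comparison uses IMI after initial exposure, and the Aim 2 regression as written uses neither later collection.
- That the plan has no visit windows at all. That can be said only of the readable text, since Figure 6 and Table 5 cannot be seen.

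This should be corrected, but it does not undermine the primary analysis.

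**What to change.** In SAP Aim 1, Outcomes Measures:

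- Collect the IMI from every randomised subject, whether or not still practising, by telephone or the existing video link.
- Take Collection 3 at session 12 or at a stated calendar backstop counted from the first session, whichever comes first. As an illustration, a day-28 backstop would apply to anyone practising fewer than 3 times a week.
- Take Collection 4 at week 12 (± 1 week) from the first session, in place of the undefined final session. Week 12 follows the SAP's programme length; the protocol's three to twelve months must be reconciled with it.
- Record sessions completed and elapsed days at each collection, and say how IMI values still missing will be handled.
- Reconcile the Aim 1 schedule with the Aim 3 timing of Table 4 measures and with Figure 6. Reconcile the numbering too: Aim 2 takes IMI from Data Collection 1, while Aim 1 first measures it at Collection 2.

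The cost is SAP wording, a reminder and a call over channels already in use, with no extra visit. The small downside is that subjects measured at the backstop will have had fewer sessions, and some will be rating an activity they have stopped. Some of those may decline, so selection is reduced but not removed.

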**Subjects:** This will be a randomized, blinded study. The same subjects will be utilized for all three aims. Upon IRB approval 30 persons with chronic strokes will be recruited from the outpatient rehabilitation department of JFK Medical Center, its hospital based fitness center program for persons with stroke and its stroke support group. **Inclusion criteria** are a) 25-85 years old, b) unilateral stroke, c) score of 24 or greater on the Folstein Mini-Mental Status Exam(52), d) Score of 1 or better on extinction and inattention portion of NIH Stroke Scale (NIHSS)(53), e) Fugl-Meyer (FM) between 30-60/66 (54), f) Score of 1 or better on language portion of NIHSS, g) intact cutaneous sensation (e.g. ability to detect <4.17N stimulation using Semmes-Weinstein nylon filaments(55). **Exclusion criteria are:** Orthopedic issues that would limit the ability to perform regular upper extremity activity. **Randomization:** Because level of impairment may affect (a) compliance with training regime, (b) intrinsic motivation, (c) adherence, and finally (d) measures of effectiveness, it is crucial (especially in a study with limited n) to balance the treatment and control arms. Because simple randomization of subjects to arms may not result in a balanced design, and because the ability to statistically adjust for baseline arm differences in these two characteristics is likely to be limited, we will use the following strategy to ensure arm equivalency. Subjects' initial scores on our measurement of motor control impairment caused by the stroke the (UEFMA) will be dichotomized into low/high. Subjects are then classified into the cell corresponding to their impairment level. Subjects in each cell (n1, n2) are provided random IDs (to prevent an ID by case recruitment association), and an investigator blinded to the randomization process then randomly assigns the first case in each cell to treatment or control arm. Each following subject within the cell is then assigned sequentially to the alternate arm. This is done for all cells to balance the source of variability between arms. **Blinding: Subjects** will be blinded to the purpose of the study and group assignment. They will also be blinded to their previous self-reported scores and their previous performance on objective tests. **Research assistants** performing outcomes measures will be blinded to group assignment and blinded to previous performance on all tests.

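### The SAP balances arms on UEFMA but the stated Aim 1 analysis has no UEFMA term; if UEFMA is prognostic, the first-exposure IMI comparison is conservative and loses power

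*SAP*

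**What the plan says.** In the SAP, the Subjects paragraph under Aim 1 plans that "30 persons with chronic strokes will be recruited". Its randomization text gives the reason for balancing: "level of impairment may affect (a) compliance with training regime, (b) intrinsic motivation, (c) adherence, and finally (d) measures of effectiveness". Subjects' "initial scores on our measurement of motor control impairment caused by the stroke the (UEFMA) will be dichotomized into low/high"; the first case in each cell is allocated at random, and "Each following subject within the cell is then assigned sequentially to the alternate arm". The same text explains why it relies on allocation: "the ability to statistically adjust for baseline arm differences in these two characteristics is likely to be limited".

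The Aim 1 Statistical Analysis paragraph names three things: a comparison of IMI scores after first exposure (the primary outcome), a group-by-time interaction for change, and a baseline check, "Baseline group equivalence will be evaluated via t-test". It names no UEFMA or stratum term, and does not say which variable the baseline test uses.

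On timing, Aim 1 Outcomes Measures says "IMI data will be measured following the first training session (Collection 2"), with later measurements after the twelfth and the final session. The Aim 2 analysis instead uses IMI from Data Collection 1. Aim 3 has every Table 4 measure, and IMI is in that table, collected before training.

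**The concern.** The reason for balancing on UEFMA is also the reason to put it in the model. Balanced allocation removes most of the between-cell UEFMA variation from the arm difference. An unadjusted test leaves that variation in its standard error, which is then too large for the design. At about 15 per arm there is little power to spare.

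The baseline t-test does not fill the gap. Under random allocation it tests a hypothesis known to be true. A non-significant result in a sample this small does not establish equivalence, and neither result says whether a covariate is prognostic, which is what decides whether adjusting helps.

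There is a further problem if IMI is first measured after the first session and that score is taken as baseline: the t-test would then be the primary comparison itself, and the early difference that the SAP predicts could be read as imbalance.

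**Working it through.** **Inputs from the documents.** N = 30 in two arms; UEFMA split low/high; alternation within each cell after a random first case (SAP, Aim 1). Significance level 0.05 (Protocol 3.3; the SAP text supplied gives none). The documents give no UEFMA-outcome correlation, and the supplied SAP text gives no power figure for N = 30, so there is no stated figure to reproduce.

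**Assumptions.** Equal split, so 15 per arm; two-sided test; cut at the median of a normally distributed UEFMA; outcome SD 1; effect 0.8 SD; correlation ρ from 0 to 0.7.

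**Step 1: unadjusted power at ρ = 0.** Noncentrality = 0.8 / √(2/15) = 0.8 / 0.365 = 2.19 on 28 df, critical value 2.048. Power = 56%. The same figure bears on the baseline t-test: it would miss a 0.8 SD difference 44% of the time.

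**Step 2: why the unadjusted test is conservative.** A median split of a normal covariate explains a share (2/π)ρ² of the outcome variance. With balance within cells, the true standard error of the arm difference is about k = √(1 − (2/π)ρ²) times what the unadjusted test assumes, so its type I error is about 2·P(T₂₈ > 2.048/k).

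- ρ = 0.3: k = √(1 − 0.057) = 0.971; 2.048/0.971 = 2.11; type I error 4.4%.
- ρ = 0.5: k = √(1 − 0.159) = 0.917; 2.048/0.917 = 2.23; type I error 3.4%.
- ρ = 0.7: k = √(1 − 0.312) = 0.829; 2.048/0.829 = 2.47; type I error 2.0%.

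**Step 3: simulation of the SAP scheme** (alternation within cells, N = 30, effect 0.8 SD). Rounded results:

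| Assumed ρ | Type I error, unadjusted | Power, unadjusted | Power, stratum in model | Power, continuous UEFMA |
|---|---|---|---|---|
| 0 | 5.0% | 56% | 56% | 55% |
| 0.2 | 4.7% | 56% | 57% | 57% |
| 0.3 | 4.4% | 56% | 59% | 60% |
| 0.5 | 3.5% | 56% | 63 to 64% | 68% |
| 0.7 | 2.0% | 57% | 72% | 84% |

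Both adjusted tests hold their type I error at about 5%. The simulated errors agree with Step 2.

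**Step 4: how much of the gain comes from the stratum.** At ρ = 0.7 the total gain is 84 − 57 = 27 points. The stratum alone gives 72 − 57 = 15, and the other 12 come from using UEFMA as a continuous score.

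**Step 5: dependence on the allocation scheme.** Under unstratified 1:1 allocation at ρ = 0.5, the unadjusted test has type I error 5.1%, so it is not conservative. At an effect of 1.06 SD (80% power for a plain t-test at 15 per arm), unadjusted power is 80.1% unstratified and 81.4% under the SAP scheme. Stratifying therefore does no harm; what is lost is the further gain from adjusting (86.3% with the stratum under the SAP scheme).

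**The case against.** **The loss is conditional.** The SAP says only that impairment may affect these outcomes. At ρ = 0 adjusting gains nothing, and at 0.2 about 1 point. Entry is limited to Fugl-Meyer 30 to 60 of 66, and a restricted range tends to weaken correlation. Nothing in the documents supports 0.7 for IMI. This stands, and it is why the range starts at zero.

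**The SAP made a choice.** It expected adjustment to be of limited use and relied on allocation. That justifies balancing, but it is a weak reason to leave the factor out afterwards: one covariate is affordable with 30 subjects.

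**The figures do not extend to the interaction.** Stable level differences between subjects cancel in a group-by-time test, so only UEFMA's correlation with change matters there. This stands; the table applies to the single-time IMI comparison.

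**Stronger readings that the documents do not support.**

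- A reader might infer that no SAP arm comparison adjusts for UEFMA. Table 5, cited as the summary of planned comparisons, and any Aim 3 analysis are not in the supplied text, and the Aim 2 regression of total time on IMI is not an arm comparison. The absence is shown only for the stated Aim 1 analysis.
- A reader might infer that no pre-exposure IMI exists. Aim 1 points that way, but Aims 2 and 3 point the other way.
- A reader might infer that the baseline t-test will cause a true effect to be dismissed. The tested variable is not named and nothing is made to depend on the result. The test is uninformative; harm is not shown.

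**Conclusion.** The point holds for the stated Aim 1 analysis. The SAP balances on UEFMA as potentially prognostic, names no UEFMA term, and plans a baseline t-test that cannot settle equivalence or the need to adjust. If UEFMA is prognostic, the comparison of IMI after first exposure is conservative and has less power than an adjusted one. This is a matter of efficiency: the omission does not inflate alpha or bias the estimate.

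The power forgone relative to continuous UEFMA is nil at ρ = 0, about 1 point at 0.2, 4 at 0.3, 12 at 0.5 and 27 at 0.7. This rests on 15 per arm, a 0.8 SD effect, a median split and the SAP's allocation scheme. The Protocol (section 3) describes computerized randomization with no strata; under that scheme the conservatism disappears, although adjustment would still add power at ρ = 0.5.

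**What to change.** 1. In the Aim 1 Statistical Analysis, prespecify entry UEFMA, preferably as a continuous score, as a covariate in the comparison of IMI after first exposure.
2. In the other arm comparisons, confirm that UEFMA is included or add it, together with the outcome's own pre-training value where one exists.
3. Delete the baseline t-test and describe baseline characteristics by arm instead.
4. Reconcile the IMI schedule: Aim 1 starts it after the first session as Collection 2, Aim 2 uses Data Collection 1, and Aim 3 has all Table 4 measures taken before training. State whether a pre-exposure IMI exists.
5. Reconcile the SAP's stratified allocation with the Protocol's unstratified description, since the analysis should follow the scheme used.

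The cost is SAP wording and one degree of freedom. UEFMA is already collected for allocation. If it proves not to be prognostic, the loss is under 1 point of power (56.2% to 55.5% at a 0.8 SD effect).

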these steps: 1) A trained interviewer will ask open-ended questions in telephone interviews, allowing participants to reflect on and describe their experiences. 2) Investigators will read participants' narratives to develop a general sense of the subjects' experiences and attitudes toward the rehabilitation program. 3) Investigators will identify emerging narrative themes in participants' experiences and attitudes toward the program. 4) Finally, an iterative coding process will be used to refine initial findings and synthesize these themes.

*Statistical Analysis:* (See Table 5 for a summary of all planned comparisons.) Linear regression will be used to evaluate the effects of IMI (From Data Collection 1) on total time (Collected during training sessions).

**Aim 3: To test the impact of motivation enhanced, game-based interventions on the effectiveness of a telerehabilitation exercise program in persons with strokes.**

*Rationale:* Studies of clinic based interventions targeting hand function in persons with stroke have produced measurable changes in hand function that do not substantially reduce hand related disability. Study of a long term, home based program emphasizing adherence will inform the development of sustainable alternatives to costly clinic based interventions that fall short of the ultimate goal of rehabilitation.

*Hypothesis:* We predict that subjects in the ME group will demonstrate larger improvements in hand function as measured by the Action Research Arm Test (ARAT) than those performing UC interventions. We further predict that subjects in the ME group will demonstrate larger reductions in impairment and larger improvements in measures of motor control and quality of life than UC group subjects.

*Subjects:* The same subjects will be utilized for Aims 1-3.

*Outcome Measures:* (Please see Table 4 for the full listing and description of the proposed clinical and quality of life measures.) A trained RA, blinded to group assignment will collect all outcome measures described in Table 4 immediately prior to training, immediately after training and 3 months after training (Data Collections 1 and 2). The RA will be blinded to previous test scores during post testing and retention testing.

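### SAP Aim 1: the group-by-time interaction does not test whether the enhanced arm's IMI advantage lasts, and the Aim 1 text names no other test for that prediction

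*SAP*

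**What the plan says.** SAP Aim 1, Hypotheses, makes two statements about level. The ME group "will report higher initial levels of motivation as measured by the Intrinsic Motivation Inventory" than the UC group, and then: "We further predict that IMI scores for the ME group will remain higher than those for the UC group".

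The Aim 1 Outcomes Measures paragraph sets three occasions: "IMI data will be measured following the first training session (Collection 2"), "as well as after the twelfth session (Collection 3) and after the final training session (Collection 4").

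The Aim 1 Statistical Analysis paragraph names three analyses:

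- "Our primary outcome measures will compare differences in IMI scores after the initial exposure to the training program".
- "Baseline group equivalence will be evaluated via t-test", with no variable named.
- "The within-and-between group interaction will be examined to evaluate differences in change between groups".

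The paragraph refers to Table 5 for the planned comparisons. That table is not in the text available. Under Aim 2 the timing differs: "Linear regression will be used to evaluate the effects of IMI (From Data Collection 1) on total time". The Aim 3 Outcome Measures text has all Table 4 measures taken before training, and Table 4 includes the IMI.

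**The concern.** The second prediction says that ME is above UC at the later collections. The interaction asks something else: whether the ME-UC difference varies between collections. Because the first listed IMI is taken after a session with the assigned games, and the plan predicts that the arms already differ there, measuring change from that point subtracts out the predicted effect.

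At stake is whether the second Aim 1 hypothesis can be answered. A non-significant interaction fits a lasting advantage, no advantage at any time, or too few subjects. A significant one fits an advantage that grew, one that shrank but is still present, or one that vanished. None of these outcomes says whether ME was higher at Collections 3 and 4.

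**Working it through.** The SAP text available gives no effect size, SD or power for the IMI, so there is no planned figure to reproduce.

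**Inputs from the documents.** 30 subjects (SAP Aim 1, Subjects); alternating allocation within impairment cell, so close to 1:1; three IMI occasions, all after exposure. The 0.05 level appears only in Protocol section 3.3, for the Wolf test.

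**Assumptions not in the documents.** n = 15 per arm, SD 1 at each occasion, compound symmetry with correlation ρ, two-sided 0.05, no dropout, and an ME advantage in SD units as shown.

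**Step 1: interaction.** Let d_t be the ME-UC difference at occasion t, and d̄ its mean over m = 3 occasions. The F test has m − 1 = 2 and (2n − 2)(m − 1) = 28 × 2 = 56 degrees of freedom, with noncentrality

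λ = (n/2) × Σ(d_t − d̄)² / (1 − ρ).

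For a constant advantage every d_t equals d̄, so the sum is 0 and λ = 0, whatever the advantage or the correlation. The rejection rate is then alpha, 5%. A simulation of 20,000 trials at ρ = 0.5 gave 0.049 for a constant 0.8 SD and 0.050 for 1.2 SD.

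**Step 2: a contrast that matches the prediction.** The mean of Collections 3 and 4 has variance (1 + ρ)/2 per subject, so the arm difference has standard error √[(1 + ρ)/2 × 2/15] = √[(1 + ρ)/15]. This is 0.306 at ρ = 0.4 and 0.346 at ρ = 0.8. With 28 degrees of freedom:

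| Constant advantage | Noncentrality, ρ = 0.4 / 0.8 | Power, ρ = 0.4 / 0.8 | Interaction |
|---|---|---|---|
| 0.5 SD | 1.64 / 1.44 | 35% / 29% | 5% |
| 0.8 SD | 2.62 / 2.31 | 71% / 61% | 5% |
| 1.0 SD | 3.27 / 2.89 | 89% / 80% | 5% |

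**Step 3: advantage not constant.** Results are for ρ from 0.3 to 0.7.

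- Differences 0.8, 0.4, 0 (advantage lost): the sum is 0.32, λ = 7.5 × 0.32/(1 − ρ) = 3.43 to 8.0, power 0.35 to 0.69.
- Differences 0.8, 0.6, 0.4 (shrinking, ME still higher): the sum is 0.08, λ = 0.86 to 2.0, power 0.12 to 0.22.
- Differences 0.4, 0.6, 0.8 (growing): the same sum, so the same λ and the same power.

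Of these patterns, the interaction is most likely to reject in the one where the prediction fails. It does not separate growth from decline.

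**Step 4: if a pre-training IMI entered the model.** With differences 0, 0.8, 0.8, 0.8, d̄ = 0.6 and the sum is 0.36 + 3 × 0.04 = 0.48. The test now has 3 and 84 degrees of freedom, λ = 7.5 × 0.48/(1 − ρ) = 5.14 to 12.0, and power is 0.43 to 0.82. But differences 0, 0.8, 0, 0, where the advantage is gone by the later collections, have d̄ = 0.2 and the same sum, 0.36 + 3 × 0.04 = 0.48. The test therefore has the same power for a lasting advantage and for a transient one.

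**The case against.** Four points can be made for the plan.

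**Table 5.** The SAP says its planned comparisons are summarised there, and the table is not in the text available. A reader might infer that the plan contains no test of the later difference. The documents do not support that. What can be said is that the Aim 1 analysis text names none.

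**The primary comparison.** A reader might infer that a fully successful trial would be reported as showing no difference between groups. That does not follow. The comparison after initial exposure is a test of level. With a 0.8 SD difference and 15 per arm, its noncentrality is 0.8/√(2/15) = 2.19, which gives about 56% power. The SAP also describes the interaction as concerning change, so a null result there would properly be read as no difference in change.

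**A lasting advantage need not be constant.** This is correct: the zero in Step 1 is exact only for a constant difference. It does not rescue the interaction. Step 3 shows that a non-constant advantage can produce a rejection, but the rejection does not say whether ME is still above UC.

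**Timing of the first IMI.** Aim 2 refers to an IMI from Data Collection 1, and the Aim 3 text implies one before training. With such a value in the model the interaction would not be zero. The Aim 1 schedule, however, is explicit, and it ties the IMI to the experience of using the simulation, which favours the post-exposure reading. Under the other reading, Step 4 shows that the interaction still does not isolate Collections 3 and 4.

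The 5% against 61-71% contrast also compares tests of two different hypotheses, at an advantage that the documents do not give. It shows the mismatch and is not a forecast of this trial's power.

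**Conclusion.** The concern holds for the second Aim 1 prediction only. The analysis named for the later collections answers a different question from the one the hypothesis asks. For a constant advantage its power equals alpha; this is algebra and needs no assumption about SD or correlation. The 61-71% for the averaged later difference does rest on the assumptions in the working, and it falls to 29-35% at 0.5 SD. Nor would a non-significant interaction in 30 subjects show that the advantage lasted. The conclusion is subject to the content of Table 5 and to reconciling the IMI collection numbers.

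**What to change.** In SAP Aim 1, Statistical Analysis, name the test for the second prediction: the ME-UC difference in mean IMI over Collections 3 and 4, taken from the same repeated-measures model, with an estimate and confidence interval at each collection. Keep the interaction as a description of how the difference changes. If Table 5 already lists this contrast, align the Aim 1 text with it.

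Reconcile the IMI timing across Aims 1, 2 and 3 (first at Collection 2, or also at Data Collection 1), and state which IMI values enter the model.

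The cost is one sentence for the contrast and a correction to the collection labels. On the Aim 1 schedule it needs no new data, visits or model.
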